Appendix 8 - 16S Gut Microbiome rRNA Analysis

The bacterial communities living in and on our bodies interact with our epithelial cells and can influence adaptive immunity, metabolic functions, and inflammation at a local and systemic level. The gut microbiota has been particularly well-studied and regulates the barrier functions of the gut epithelium, prevents pathogen or pathobiont overgrowth, facilitates metabolism of dietary fibers, and regulates metabolism. The gut microbiota may also influence the initiation, progression, and treatment of cancer. Monitoring the microbiota in patients may enhance our ability to predict the likelihood of a positive patient response to therapy as well as indicators of adverse treatment effects and sensitive metrics of general patient health. Given the possibility of altering the microbiome of a patient, future research is likely to include manipulating microbiotic communities to maximize the effectiveness of other therapies.

Fecal samples are relatively easy to collect and non-invasive. They provide an indication of the gut microbiome which may be an indicator of general health, impact drug availability, and indicate the presence of communities associated with inflammation, digestive inefficiencies, and pathogens. Monitoring the gut microbiome may allow us to predict the risk of possible side effects of pembrolizumab (colitis and decreased appetite) and paricalcitol (decreased appetite).

Sample processing. Quantitative TaqMan PCR assay will be used that targets Variable Regions 3 and 4 of the 16S rRNA sequence. This assay will provide a rough estimation of the overall bacterial load per sample. It is important to recognize that different species have different copy numbers of the *rrs* gene that encodes the 16S rRNA, however this assay will still provide a rough estimation of bacterial load for inter-sample comparisons. For whole community surveys, 515F/806R 16S rRNA primers will be used to amplify Variable Regions 4 and 5. This primer pair achieves nearly universal coverage across bacteria and archaea⁷. These amplicons will be sequenced using the Illumina MiSeq, NextSeq, or HiSeq next generation sequencing platforms. For the purposes of this work, the throughput, cost, and depth of coverage provided by the Illumina MiSeq currently make this sequencing platform better suited than other technologies. Moreover, the read lengths of up ~300bp allows approximately genus, and sometimes even species-level discrimination of taxa.

Sequence Analyses. The microbial communities will be compared using phylogenetic beta diversity metrics based on 16S rRNA reads. The 515F/806R 16S rRNA primers will amplify a 292bp region containing variable regions 4 and 5. Sequences will be processed using the open source Quantitative Insights Into Microbial Ecology 2 (QIIME2) software package to demultiplex, quality filter, and cluster sequences into operational taxonomic units (OTUs). Taxonomy will be assigned to OTUs by classification against the Greengenes database using the RDP Classifier (unless a better approach is available at the time of analysis). These data will be used to understand the differences in taxonomic composition.

Measuring diversity within and between samples. Beta diversity is a measure of the relative similarity of samples (i.e., the between-sample diversity), while alpha diversity is a measure of the diversity within a sample. Thus beta diversity will provide an estimate on how different

microbial communities are, while alpha diversity provides information on the richness or evenness of a single community. Both alpha and beta diversity measures can be qualitative, considering only presence/absence of taxonomic groups in a community, or quantitative, considering the abundance of taxonomic groups. Qualitative measurement of beta diversity, for example, may be simply the fraction of shared taxa, but differences may be overlooked if the same set of taxa are present but in different abundances. However, quantitative diversity metrics may be misleading as community profiling based on amplicon sequence data is not necessarily quantitatively accurate. Additionally, diversity metrics are either taxon-based or phylogenetic-based. Taxon-based diversity considers all taxa to be equally related, ignoring the likelihood that closely related taxa are phenotypically similar. Phylogenetic diversity accounts for the evolutionary relationships between taxa, and has been shown to improve the resolution of differences between microbial communities.

Appendix 9 - Fecal Swab Sample Collection Instructions (To be included in Fecal Swab Collection kit)

You have been provided a Fecal Swab Collection kit. The collection kit includes the following items:

1. Disposable Gloves
2. A stool collection bowl (toilet hat), as pictured below.

3. A bio-specimen bag
4. A pre-labeled CultureSwab tube, as pictured below. The tube has already been labeled with your assigned subject ID. **Please DO NOT write your name on the label.**

In order to ensure the best results, please follow the instructions below.

You will need to collect **two different** stool samples during each treatment cycle:

1. The **first** stool sample is to be collected up to 72 hours **before** your study treatment on day 1 of each treatment cycle.
2. The **second** stool sample is to be collected from your first or second bowel movement within 24-72 hours **after** receiving your study treatment on day 1 of each treatment cycle.

A **final** stool sample will be collected approximately 30 days after your last dose of study treatment.

To Collect a Stool Specimen:

1. Raise the toilet seat and place the stool collection container (toilet hat) on the back of toilet bowl. Place the toilet seat down.
2. Pass stool into the stool collection container. Do not urinate into the container.
3. Put the provided disposable gloves on before collecting the stool sample. Use the provided CultureSwab to remove a portion of the stool, as follows:
 - a. Remove the CultureSwab tube from the plastic bag.
 - b. Remove the sterile swab from the tube while handling only the cap and not touching the swab or shaft.
 - c. Wipe the sterile swab across the stool to collect a pea size amount of stool on the tip of the swab. Do not touch the swab on the sides of the collection bowl or on any other surface.
 - d. Carefully re-insert the swab with the fecal sample back into the CultureSwab tube and close with the cap.
4. Write the date and time of collection on the label that is affixed to the tube. DO NOT write your name on the tube.
5. Dump the remaining stool in the toilet and flush. The stool collection bowl and the disposable gloves may be disposed in the regular trash. Wash your hands thoroughly with soap and water.
6. Store the CultureSwab tube in the bio-specimen bag in the FREEZER.
7. Return the sample to the study team within 24-72 hours of collection. This should correspond with your next study visit. Sample can be transported in the car without need for ice packs, if the car is air-conditioned. If the car is not air-conditioned please transport the specimen on ice to keep cool.

IMPORTANT: If for some reason you cannot make your scheduled appointment within 72 hours of the fecal collection, please contact your study site at (site to specify contact tel number) to make arrangements for return of the sample.

If you have any questions please call (site to specify contact tel number)

Thank you for your participation!

Statistical Analysis Plan (SAP) – Clinical Endpoints

A SU2C CATALYST® RANDOMIZED PHASE II TRIAL OF THE PD1 INHIBITOR PEMBROLIZUMAB (KEYTRUDA®) WITH OR WITHOUT A VITAMIN D RECEPTOR AGONIST PARICALCITOL (ZEMPLAR®) IN PATIENTS WITH STAGE IV PANCREATIC CANCER WHO HAVE BEEN PLACED IN BEST POSSIBLE RESPONSE (WITH NO FURTHER IMPROVEMENT IN THEIR TUMOR)

[Clinicaltrials.gov: NCT03331562](https://clinicaltrials.gov/ct2/show/NCT03331562)

July 10, 2020

1 INTRODUCTION

The 5-year survival rate for pancreatic ductal adenocarcinoma (PDA) is only 8%, as detection is usually very late in the disease, most patients are not eligible for potentially curable resection, and those with resection usually experience fatal reoccurrence within 2 years. There are some new treatments that improve survival for patients with stage IV PDA, but keeping patients in partial or complete remission is a major challenge. A maintenance regimen based on a vitamin D receptor (VDR) agonist, paricalcitol, could improve the activity of an immune checkpoint inhibitor, pembrolizumab. The combination regimen of paricalcitol + pembrolizumab is hypothesized to give benefit for maintenance of remission for patients with advanced pancreatic cancer (over pembrolizumab alone).

2 DATA SOURCE

Datasets will come from the phase II clinical trial titled: A SU2C Catalyst® Randomized Phase II Trial of the PD1 Inhibitor Pembrolizumab (Keytruda®) with vitamin D receptor agonist Paricalcitol (Zemplar®) in Patients with Stage IV Pancreatic Cancer Who Have Been Placed in Best Possible Response (with no further improvement in their tumor).

3 ANALYSIS OBJECTIVES

The primary objective is to determine whether combined paricalcitol + pembrolizumab reduces disease progression compared to pembrolizumab alone among patients with stage IV pancreatic cancer who have been put in best response.

The primary endpoint is the percent of patients with radiographic disease progression according to RECIST 1.1 at 6 months.

Secondary objectives include:

- (1) Evaluate the toxicity of the combination of paricalcitol + pembrolizumab versus pembrolizumab alone.
- (2) Evaluate the difference in overall survival in patients administered the combination of paricalcitol + pembrolizumab versus pembrolizumab alone.

Exploratory objectives include:

- (1) Evaluate the difference in disease progression according to iRECIST vs. RECIST 1.1 criteria.

4 ANALYSIS SETS/ POPULATIONS/ SUBGROUPS

This trial will have 24 patients randomized to paricalcitol + pembrolizumab (n=12) or pembrolizumab alone (n=12). No stratification will be performed.

5 ENDPOINTS AND COVARIATES

Primary endpoint: Percent of patients with radiographic disease progression according to RECIST 1.1 at 6 months, defined as 180 days from initial treatment (C1/D1).

Secondary endpoints:

- (1) Incidence of toxicities
From initial treatment to end-of-treatment
- (2) Overall survival
Time from initial treatment to death

Exploratory endpoints:

- (1) Disease progression according to RECIST 1.1 versus iRECIST criteria
Percent of patients with radiographic disease progression at 6 months

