6.2 Assessing and Recording Adverse Events

An adverse event is defined as any untoward medical occurrence in a patient or clinical investigation patient administered a pharmaceutical product and which does not necessarily have to have a causal relationship with this treatment. An adverse event can therefore be any unfavorable and unintended sign (including an abnormal laboratory finding, for example), symptom, or disease temporally associated with the use of a medicinal product or protocol-specified procedure, whether or not considered related to the medicinal product or protocol-specified procedure. Any worsening (i.e., any clinically significant adverse change in frequency and/or intensity) of a preexisting condition that is temporally associated with the use of the pembrolizumab and /or paricalcitol, is also an adverse event.

Adverse events may occur during the course of the use of pembrolizumab and/or paricalcitol in clinical trials, or as prescribed in clinical practice, from overdose (whether accidental or intentional), from abuse and from withdrawal.

Progression of the cancer under study (pancreatic cancer) is not considered an adverse event.

All adverse events that occur after the consent form is signed but before treatment allocation/randomization must be reported by the investigator if they cause the patient to be excluded from the trial, or are the result of a protocol-specified intervention, including but not limited to washout or discontinuation of usual therapy, diet, placebo treatment or a procedure.

From the time of treatment allocation/randomization through 30 days following cessation of treatment, all adverse events must be reported by the investigator. Such events will be recorded at each examination on the Adverse Event case report forms/worksheets. The reporting timeframe for adverse events meeting any serious criteria is described in section 6.2.3.1. The investigator will make every attempt to follow all patients with non-serious adverse events for outcome.

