For the time period beginning at treatment allocation/randomization through 90 days following cessation of treatment, or 30 days following cessation of treatment if the patient initiates new anticancer therapy, whichever is earlier, any serious adverse event, or follow up to a serious adverse event, including death due to any cause other than progression of the cancer under study (reference Section 6.2.3.3 for additional details), whether or not related to the trial treatment, must be reported within 24 hours to the Sponsor. The Sponsor will report within 24 hours (working days) to Merck Global Safety.

Additionally, any serious adverse event, considered by an investigator who is a qualified physician to be related to pembrolizumab that is brought to the attention of the investigator at any time following consent through the end of the specified safety follow-up period specified in the paragraph above, or at any time outside of the time period specified in the previous paragraph also must be reported immediately to the Sponsor. The Sponsor will then report to Merck Global Safety.

All patients with serious adverse events must be followed up for outcome.

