8.3.5 Analysis of Secondary Endpoints

8.3.5.1 Analysis of Toxicities

All adverse events occurring on or after Cycle 1/day 1 will be summarized by body systems and per grade according to NCI-CTCAE Version 4. Additionally, all serious adverse events and events of clinical interest (ECI) as defined in section 6.2.3.2 will be listed separately and tabulated. All patients who receive any amount of trial treatment will be included in the analysis.

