7 STATISTICAL METHODOLOGY

7.1 STATISTICAL PROCEDURES

Primary outcome: Progression-free survival

The proportion of patients in each arm who are progression-free at 6-months will be compared using a one-sided test of binomial proportions (equivalent to a Pearson's chi-squared test). If the assumptions of the Pearson's chi-squared test are not met, Barnard's exact unconditional test of equality will be used, as implemented in StatXact.

Patients unevaluable for progression at 6-months due to a non-progression related event will be excluded from analysis.

Statistical comparison of progression-free survival between the two treatment arms will be performed using a log-rank test, with estimation of the hazards ratio using a Cox proportional hazards model. A sensitivity analysis will include patients with an outcome of death due to another cause (other than progressive disease), which will be considered a competing event for progression. Analysis will be performed using the Fine and Gray (1999) approach.

Secondary outcome 1: Toxicity

All adverse events (AE) occurring on or after C1/D1 will be summarized by body systems and per grade according to NCI-CTCAE Version 4. Additionally, all serious adverse events (SAE) and events of clinical interest (ECI) will be listed separately and tabulated. ECIs for this trial include an overdose of pembrolizumab and an elevated AST or ALT lab value, as defined in section 6.2.3.2 of the protocol. All patients who receive any amount of trial treatment will be included in the analysis. The proportion of patients in each arm with toxicity will be compared using a chi-squared test or Barnard's exact unconditional test of equality as outlined above.

Secondary outcome 2: Overall survival

Overall survival will be calculated for each arm using a Kaplan-Meier estimate. Statistical comparison of overall survival between the two treatment arms will be performed using a log-rank test, with estimation of the hazards ratio using a Cox proportional hazards model. Patients with an outcome of death due to another cause (other than progressive disease) will be considered a competing event for death. Analysis will be performed using the Fine and Gray (1999) approach.

Exploratory outcome 1: RECIST 1.1 versus iRECIST

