Rate of progression-free survival, % (95% CI)				
6 mo				
12 mo				
Median progression-free survival, mo (95% CI)				
Overall survival				
Median overall survival, mo (95% CI)				
Survival rate, % (95% CI)				
6 mo				
12 mo				

Table 3. Common adverse events of grade 3 or higher

Event	Pembrolizumab n = x	Pembrolizumab + Paricalcitol n = x	P value
Adverse event leading to death, no. (%)			
Serious Adverse Events			
Anemia			
Cataract			
Nausea			
Abdominal pain			
Diarrhea			
Vomiting			
Bloating			
Constipation			
Fatigue			
Gait disturbance			
Urinary tract infection			
AST increased			
ALT increased			
Alkaline phosphatase increased			
Arthralgia			
Pain in extremity			
Back pain			
Hypertension			

Note: these were the most common events on the Nov 2019 DSMB report (> 10% of patients)

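### SAP section 5 ends the toxicity endpoint at end of treatment, so the between-arm comparison omits later adverse events that the protocol already collects

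*SAP*

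**What the plan says.** **Analysis window.** SAP section 5, secondary endpoint (1), runs "From initial treatment to end-of-treatment". The SAP does not define end of treatment; in the protocol the EOT visit falls up to 5 days after the last dose (section 5.0 and Table 8).

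SAP 7.1 says: "All adverse events (AE) occurring on or after C1/D1 will be summarized by body systems". Protocol 8.3.5.1 says: "All adverse events occurring on or after Cycle 1/day 1 will be summarized by body systems and per grade". Both fix a start and neither fixes an end. SAP 7.1 also has all SAEs and ECIs listed separately and tabulated.

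**Between-arm comparison.** SAP 7.1: "The proportion of patients in each arm with toxicity will be compared using a chi-squared test", with Barnard's test as the alternative. The proposed "Table 3. Common adverse events of grade 3 or higher" has a P value column. Neither states a window.

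**Collection window.** Protocol 6.2 runs AE reporting "through 30 days following cessation of treatment, all adverse events must be reported by the investigator". Protocol 6.2.3.1 runs SAE reporting "through 90 days following cessation of treatment, or 30 days following cessation of treatment if the patient initiates new anticancer therapy, whichever is earlier", and 6.2.3.2 gives ECIs the same window. For SAEs judged related to pembrolizumab, 6.2.3.1 adds that those arising "at any time outside of the time period specified in the previous paragraph also must be reported immediately to the Sponsor".

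**Expected timing.** Protocol 4.2.4 says that immune-related AEs may first occur several months after the last pembrolizumab dose.

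**The concern.** Toxicity of the combination against pembrolizumab alone is the first secondary objective, and the 7.1 test and the Table 3 P values are its only formal comparisons. Followed as written, section 5 removes from them the period after treatment, which the protocol extends collection to cover. Sites would report the events and they might appear in the summaries, yet they would not count in the proportions being compared. The word all in SAP 7.1 and protocol 8.3.5.1 points to a wider window than section 5 gives, and nothing in the SAP reconciles the two.

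With 12 patients per arm, a single patient whose only qualifying toxicity comes late changes the compared proportion visibly.

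**Working it through.** The plan gives no numerical figure for the toxicity comparison, so there is none to reproduce. The power statement in protocol 8.2 concerns the primary endpoint and does not bear on this point.

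**1. Windows side by side**

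| Place | Start | End |
|---|---|---|
| SAP 5 | initial treatment | end of treatment (undefined) |
| SAP 7.1 | C1/D1 | none stated |
| Protocol 8.3.5.1 | C1/D1 | none stated |
| Protocol 6.2, all AEs | randomization | 30 days after cessation |
| Protocol 6.2.3.1 and 6.2.3.2, SAEs and ECIs | randomization | 90 days after cessation, or 30 with new anticancer therapy, whichever is earlier |

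**2. Which SAP section governs.** Section 5 also holds the time definitions for the primary endpoint (180 days from C1/D1) and for survival (initial treatment to death), and 7.1 restates neither origin. Silence in 7.1 on the toxicity end date fits that pattern, so the natural reading is that section 5 governs.

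**3. Collection time left outside.** Nominally 30 days for AEs and up to 90 days for SAEs/ECIs. The exact figure varies:
- *Anchor alone.* If collection counts from the last dose and the SAP window ends at an EOT visit on day 5, the gaps are 30 − 5 = 25 and 90 − 5 = 85 days. If collection counts from that EOT visit and the SAP window ends at the last dose, they are 30 + 5 = 35 and 90 + 5 = 95 days.
- *Visit window.* Protocol 6.1.7.4 records AEs occurring before the safety visit, due 30 ± 5 days after the last dose; Table 8 puts it 30 ± 5 days from EOT. The AE gap is then 25 − 5 = 20 to 5 + 35 = 40 days.
- *New therapy.* 6.2.3.1 shortens the SAE window to 30 days. The wording in 6.1.7.4 could end it at the start of the new therapy, in which case the gap could be close to zero.

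**4. Weight of one patient.** 1/12 = 0.083, or 8.3 percentage points.

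**5. Illustration with assumed counts** (Barnard's test, 12 per arm). Neither document sets an alpha or a sidedness for toxicity; 0.05 is used only as a familiar marker. With equal arms the two-sided value is twice the one-sided value.

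| Patients with toxicity | One-sided p | Two-sided p |
|---|---|---|
| 4 vs 0 | 0.019 | 0.038 |
| 3 vs 0 | 0.047 | 0.094 |
| 2 vs 0 | 0.110 | 0.220 |
| 4 vs 1 | 0.081 | 0.162 |
| 12 vs 11 | 0.262 | 0.523 |

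- Dropping one late patient from the higher arm, 4 vs 0 becomes 3 vs 0: two-sided p goes from 0.038 to 0.094. One-sided, it goes from 0.019 to 0.047 and stays below 0.05.
- Dropping one from the lower arm, 4 vs 1 becomes 4 vs 0: two-sided p goes from 0.162 to 0.038, the other way.
- There are 78 count pairs with one arm higher. Losing one patient from the higher arm changes the call at 0.05 in 9 of them (two-sided) or 10 (one-sided). Losing one from the lower arm also changes it in 9 or 10 pairs. The pairs are not equally likely, so these counts are not probabilities.
- If nearly every patient has a qualifying event, as in 12 vs 11, the window hardly matters.

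**The case against.** **An on-treatment window is a legitimate choice.** The arms differ only by paricalcitol, both receive pembrolizumab, the late-onset warning concerns pembrolizumab, and later events mix with subsequent therapy. This stands as a reason to keep an on-treatment analysis. It does not explain why the formal comparison should omit events that the protocol collects, and the SAP gives no such justification.

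**The safety record is preserved.** A reader might infer that late events vanish from the report. The documents do not support that: 7.1 summarises all AEs and lists and tabulates all SAEs and ECIs. Only the between-arm comparison is affected.

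**Section 5 settles the window.** A reader might infer that the window is open to choice after the data are seen. Because section 5 is where the SAP puts its time definitions, that is a lesser concern; the main one is what section 5 excludes.

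**The protocol's own collection rules.** A reader might infer that protocol 4.8 and Table 8 footnote b conflict with 6.2.3.1 because they do not mention new anticancer therapy. They do not conflict: both refer to 6.2.3.1 and so take over its rule. Two real differences in wording remain. The anchor is cessation of treatment in 6.2 and 6.2.3.1, the last dose for the safety visit in 6.1.7.4, and EOT in Table 7 footnote c and Table 8. And 6.1.7.4 words the effect of new therapy on SAE recording differently from 6.2.3.1.

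**Conclusion.** The concern holds. On the natural reading of section 5, the between-arm toxicity test and the Table 3 P values leave out nominally about 30 days of AE collection and up to 90 days of SAE/ECI collection per patient.

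The effect on the result cannot be sized, because the documents give no rates of late events. A reader might infer that the exclusion favours the combination, or that it can only hide a difference. Neither follows: both arms receive pembrolizumab, and losing a patient can move p either way. The p values above rest on assumed counts and on a threshold that the plan does not set for toxicity. The sidedness and the qualifying grade for the 7.1 test are also unstated, and fixing the window does not settle them.

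This should be corrected. It does not touch the primary endpoint, the sample size or the power.

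**What to change.** In SAP section 5, replace end of treatment with the protocol's collection period: first dose through 30 days after treatment for all AEs, and the window of protocol 6.2.3.1 and 6.2.3.2 for SAEs and ECIs. State one anchor.

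In SAP 7.1, say that this window applies to the between-arm test and to Table 3. List and tabulate separately any pembrolizumab-related SAE reported after the window. Keep an on-treatment analysis as a labelled supplement.

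Separately, reconcile the protocol's anchor wording (6.2, 6.2.3.1, 6.1.7.4, Table 7 footnote c, Table 8), and reconcile the new-therapy wording of 6.1.7.4 with that of 6.2.3.1.

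Cost: SAP wording plus a minor protocol clarification, and no new data, since the protocol already requires collection. Downside: reported toxicity rates may be slightly higher, and late events are harder to attribute to trial treatment.
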